4.2 What would make this part of the app better?

5. "Wonderful, thank you. The app also allows you to see on a graph how your symptoms may change over time [show them on tablet]. Please take a few minutes to look over this part of the app." [allow time for review]

5.1 What did you like about this part of the app?

5.2 What would make this part of the app better?

6. "Great, thanks. Now, let's look at the last part of the app. This portion allows you to receive directed guidance on ways to address the symptoms you reported in the second part of the app. For example, if you reported that you felt fatigued, the application will provide you with a brief audio clip that offers ideas to help you sleep better. Please take a few minutes to look over this part of the app." [allow time for review] As with the other parts of the app, if you notice something you like or don't like, or if something confuses you or catches your attention we would like to know about that." [allow time for review]

6.1 What did you like about this part of the app?

6.2 What would make this part of the app better?

7. "Thank you again for reviewing each part of the app. The final piece of the program is communication with the study team. This will include receiving a daily text from the study team that will remind you to log your symptoms every day. The texting feature can be found here [show them on tablet]. We've sent some examples of what the daily texts will look like."

7.1 What did you like about the text messaging?

7.2 What would make the text messaging better?

8. If you had the choice of using this program to help you better care for yourself and ultimately your child, would you want to use it? Why or why not? [if needed: How do you think you would use it? [e.g., how often, under what circumstances, etc.?]

9. "Thank you so much for your help today. Is there anything else you can think of that you would like to share with us?"

End interview, collect tablet, provide compensation.

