The PI's research, and that of others, highlights that caregivers of children with food allergy describe the physical challenges of care as overwhelming and constant. The perpetual hypervigilance and ensuing exhaustion associated with time-consuming and persistent condition-management activities – such as monitoring a child's food consumption at school or when with friends, shopping for, and preparing special food – have the greatest impact on caregiver quality of life and are associated with fatigue, uncertainty, constant stress, social isolation, reduced spontaneity, and persistent anxiety, fear, and depression.⁴⁻¹¹ Following diagnosis, caregivers experience a period of psychosocial adjustment where these symptoms are most pronounced.¹⁷ As caregivers begin to understand the necessary precautions and potential consequences of accidental ingestion associated with FIA and the required condition-management activities, fear and anxiety emerge as the predominant emotions. While a certain level of anxiety is essential for adequate management, high levels of sustained anxiety in caregivers of children with food allergy may be maladaptive, increasing the overall burden of caring for a child with FIA and negatively impacting the caregiver's ability to provide care to self, child, and family.¹⁸

B3. Self-management strategies for caregiver stress and fatigue are lacking.

Despite recognition that family caregivers of children with severe food allergies are at risk for adverse consequences, decreased quality of life, and diminished caregiving effectiveness, there are a lack of caregiver-centered self-management interventions to address stress-related fatigue, depression and anxiety symptoms. However, symptom self-management is exceedingly relevant to the caregiver of a child with newly diagnosed food allergy(ies) as management is complex and compounded by factors outside of the caregiver's control which are further intensified by the lack of definitive treatment or cure. The short-term goal of this technology-enhanced, self-management mHealth intervention is to enhance and promote effective self-management behaviors to improve the psychosocial well-being of the caregiver that in the long-term will lead to improved outcomes for the child, namely prevention of potentially fatal food induced reactions.

C. Innovation

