
D3.3. Control group

The control group will receive Component 1 of the intervention.

D3.4. Primary Aim 1a and 1b: Key informant interviews and intervention tailoring and adaptation

We will use a purposive sampling strategy to identify caregivers of children with established (≥ 1 year from diagnosis) food allergy(ies) familiar with the disease process and management. Data obtained through key informant interviews using a semi-structured protocol and a qualitative descriptive approach²¹ will inform tailoring and adaptation of FASST. The purpose of interviews will be to obtain feedback from caregivers of children with established food allergy(ies) who have been managing the condition for one year or more. Participants will be asked about their experience in the first year of managing their child’s food allergy, with specific questions regarding the first 4 weeks of management and the perceived impact on their psychosocial well-being and overall quality of life. Participants will be shown a mocked-up application on a mobile device and asked to provide feedback related to the content. At the beginning of the session, the PI will deliver detailed verbal instructions regarding use of the device and intervention components. Participants will be provided with mobile devices that have been prepared for the feasibility testing (Aim 2) with access to the FASST application and text messaging. After allowing time for participants to explore the intervention (with direct observation), the PI will ask 8-10 open-ended questions with probes using an interview guide. Questions will be designed to assess the acceptability, feasibility, and usability of the intervention. The interview will conclude with questions regarding suggested improvements to the intervention. The hands-on, observational session is expected to last 45 to 60 minutes and the interview is expected to last an additional 45 to 60 minutes. The PI will video record observations to inform adaptation of the intervention. The interview will be audio recorded and transcribed. Following data analysis (described in **D3.7.**) the results from the interviews will be used to adapt the intervention to meet the specific needs of caregivers of children ≤ 18 years-of-age with a newly diagnosed food allergy(ies).

D3.5. Primary Aim 2: Feasibility Testing

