“Thanks for agreeing to help us with our study. We’d like to ask you a few questions about our program so we can continue to improve what we’re doing.”

Parent/Caregiver Questions

1. Have you used a tablet computer, iPad, the internet, or a smartphone before?
 - 1.1 [If so] How often do you use one?
 - 1.2 [If so] When you use a tablet, iPad, the internet, or a smartphone, what types of things do you use it for?
2. Have you ever used technology such as a tablet, iPad, the internet, or a smartphone to help you manage your health or your child’s health?
[if **No**, skip to 3.] If **yes**, ask:
 - 2.1 What types of activities did you do on the tablet, iPad, internet or smartphone?
 - 2.2 How helpful was it / were they? What did you like about these activities? Is there anything you didn’t like?
 - 2.3 What would make them better?
3. “Great. Thanks. Now I’d like to ask you some questions about the activities we have for our program. Remember, there are no right or wrong answers. The things that you tell us will help us improve the activities for other parents and caregivers. There are three main parts to the program.”

“The first part uses educational materials. They are located here [show them on tablet]. Experts in food allergy created them for caregivers. You can move from one page to the next, like this [show them on tablet]. Please take a few minutes to look them over. If you notice something you like or don’t like, or if something confuses you or catches your attention we would like to know about that.” [allow time for review]

 - 3.1 What do you like about them?
 - 3.2 What would make them better?
 - 3.3 Do you think these materials would be helpful to you? [if yes, How? If no, Why not?] [if needed: How could you see yourself using them to manage your child’s health?]
4. “Thank you. The second part of the tablet activities is an app that helps keep track of how caring for a child with a food allergy may impact you. The app is located here [show them on tablet]. The app allows you to track any symptoms you may experience as someone caring for a child with a food allergy. Please take a few minutes to look over this part of the app. If you notice something you like or don’t like, or if something confuses you or catches your attention we would like to know about that.” [allow time for review]
 - 4.1 What did you like about this part of the app?

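### Interview guide item 8, the only direct willingness-to-use question, presents the program as helping caregiver and child before asking, and its probe covers only use; items 5 and 7 lack the invitation to voice dislikes

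*Combined protocol and SAP*

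**What the plan says.** Aim 1a (Specific Aims) uses interviews with 10 caregivers of children with established food allergy to find ways of making the app more acceptable. Section D3.4 says that "the PI will ask 8-10 open-ended questions with probes using an interview guide" and that the questions are meant to assess acceptability, feasibility and usability.

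The script is the Interview Guide for Caregivers of Children with Food Allergy(ies). Items 3 to 7 take the informant through the parts of the program. Item 8 then puts the question of willingness in these words: "using this program to help you better care for yourself and ultimately your child, would you want to use it". It goes straight on to ask for reasons on either side. An if-needed probe follows: "How do you think you would use it", with how often and in what circumstances given as examples. Item 9 is an open closing question.

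Other parts of the guide also bear on balance:
- Item 3 tells the informant: "Remember, there are no right or wrong answers".
- Item 3.3 asks, of the educational materials only: "Do you think these materials would be helpful to you? [if yes, How? If no, Why not".
- Item 2.2 asks "Is there anything you didn’t like", but about technology the caregiver has used in the past, not about FASST.

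**The concern.** A question meant to find out whether people would use something should not tell them, in its stem, what good it is supposed to do. Here the stem links the program to better self-care and, in the end, to better care of the child. A parent who says no is turning down something just framed as helping their own child. The principal investigator asks the question in person, a setting that can itself favour agreeable answers. The prepared follow-up then explores the manner of use and has no counterpart on non-use.

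The benefit is not established at this stage. Section B3 describes caregiver well-being as the short-term goal, one "that in the long-term will lead to improved outcomes for the child", and the section on potential benefits speaks only of potential. What is at stake is the usefulness of the interviews for adapting the app. With 10 informants, each account of why someone would not use it, or would stop, is worth having before the 30-caregiver trial begins.

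**Working it through.** No arithmetic applies. The plan attaches no rate, threshold or decision rule to item 8, and it gives no estimate of a wording effect. The check is a reading of every item in the guide.

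**Step 1. Is item 8 the only direct willingness question?** Yes. The nearest other item is 3.3, which asks about perceived helpfulness and covers the educational component alone.

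**Step 2. How is item 8 built?** It has three parts, in this order:
1. a conditional containing a purpose phrase that presupposes benefit to caregiver and child;
2. a closed question on wanting to use the program;
3. a request for reasons in either direction.

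The optional probe comes last and assumes use. The framing therefore precedes the answer and the balanced request follows it. An informant nudged toward yes will mainly be explaining a yes.

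**Step 3. How balanced are the items on the program itself?**

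| Item | Subject | Lead-in invites dislikes as well as likes? | Sub-questions |
|---|---|---|---|
| 3 | Educational materials | Yes | Liked; improve; helpful (two-sided) |
| 4 | Symptom tracking | Yes | Liked; improve |
| 5 | Symptom graph | No | Liked; improve |
| 6 | Directed guidance | Yes | Liked; improve |
| 7 | Daily texts | No | Liked; improve |

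The invitation is scripted for 3 of the 5 items. No numbered sub-question in items 3 to 7 asks outright what was disliked; the one that does is 2.2, on past technology. Item 7 is a notable gap because D3.2 makes the daily text a recurring contact in the intervention arm.

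**Step 4. Where do the answers go?** Under D3.7, Aim 1 interviews are coded into themes by conventional content analysis, and the themes guide adaptation. Table 1 (D3.5) measures Aim 2 acceptability by caregiver satisfaction and by the number and types of problems reported. Item 8 does not enter those measures.

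**The case against.** The strongest reply is that item 8 does not stop at yes or no: every informant is asked why or why not. The phrase about helping is a statement of purpose inside a conditional, not a claim that benefit has been shown. It matches the order of effects in B3, and only one thing is being asked, namely whether they would use the program. Around it, the guide says that no answer is wrong, invites dislikes at items 3, 4 and 6, has a two-sided question at 3.3, asks of each part what would improve it, and closes openly. Item 6 also refers back to the other parts of the app, which could be taken to cover the graph. Adaptation draws on directly observed, video-recorded use as well (D3.4).

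Most of this stands, and it limits the point to a small one. It does not remove it. The request for reasons comes after the framed answer, the statement on right and wrong answers is made once at item 3, and nothing in the script balances the use-only probe or supplies the invitation at item 7.

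A reader might infer more: that the stem suppresses reasons for non-use, inflates an acceptability rate, or lets barriers pass unnoticed into Aim 2. The documents do not support this. Reasons for non-use are asked for, and people who say yes can also voice barriers in items 3 to 7. No share answering yes is planned. Aim 2 acceptability has its own measures. The post-intervention interviews in D3.5 also use a guide, but the documents do not say that it is this one.

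**Conclusion.** The point holds as a minor one on wording. Item 8 leads mildly toward yes, its only probe looks at use, and items 5 and 7 lack an invitation that their neighbours have. The direction is a reasonable inference from the wording. The size cannot be derived from the documents, and any percentage shift or count of lost refusals would be invented. The conclusion assumes that interviewers follow the script closely; in a semi-structured interview a skilled interviewer may supply the missing balance unprompted. It concerns the quality of the Aim 1a qualitative feedback only. No numerical effect and no bias in the Aim 2 acceptability measures is claimed.

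**What to change.** Three changes to the Interview Guide:

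1. Reword item 8 without the purpose phrase: *If this program were available to you, would you use it or not? Why or why not?*
2. Beside the existing probe on frequency and circumstances of use, add: *What might keep you from using it, or make you stop?*
3. Extend to items 5 and 7 the invitation to mention likes, dislikes and points of confusion that already introduces items 3, 4 and 6.

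The cost is a minor amendment to the guide. The added probe and the two lead-in sentences take little time in an interview planned for 45 to 60 minutes. Sample size, measures and analysis do not change.
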